ID RCB : not applicable

Sponsor ID : QS-NIS-G-H-2101

Title of document : Protocol synopsis

Date: 03-OCT-2022

Version: 2.0

POST MARKET FOLLOW-UP STUDY OF A ROBOTIC DEVICE FOR IMAGE-GUIDED PERCUTANEOUS NEEDLE PLACEMENT IN THE ABDOMEN

| | |
|---|--|
| Study title | Post Market Clinical Follow-up study of a robotic device for image-guided percutaneous needle placement in the abdomen |
| Study Number | QS-NIS-G-H-2101 |
| Investigational product | EPIONE® device |
| Investigational product characteristics | The device is a user controlled, stereotactic accessory intended to assist in the planning and manual advancement of needle, as well as in verification of needle position during CT-guided percutaneous ablation procedures. |
| Investigational device administration | The operating principle of the investigational device is the following: pre-interventional CT-scan acquisition, planning with the device's software , needle's insertion according to the predefined planning, acquisition of a per-procedure CT-scan to evaluate the needle(s) placement. |
| Reference therapy/product | N/A |
| Study design | Post Market Clinical Follow-up study (PMCF) Non-interventional, prospective, non-comparative study |
| Number of sites & country | 1 site in France |
| Sample size | Around 55 patients Around 55 CT-guided procedures in the abdomen |
| Indication | Percutaneous CT-guided procedures (tumor ablation, biopsy, ...) in the abdomen (liver, kidney, ...) |

ID RCB : not applicable

Sponsor ID : QS-NIS-G-H-2101

Title of document : Protocol synopsis

Date: 03-OCT-2022

Version: 2.0

| | |
|--------------------------------------|--|
| Primary objective | Evaluation of the technical success of the device |
| Primary endpoint | Number of targets reached; the target is considered to have been reached when the needle is positioned accurately enough to allow the planned procedure to be performed. |
| Secondary objective | Assessment of performance parameters and safety |
| Secondary endpoint | 
Performance parameters
 
○ Assessment of the needle placement accuracy○ Assessment of the needle adjustments to reach the target○ Assessment of post-intervention ablation success○ Assessment of local tumor recurrence,○ Operator satisfaction through a 5-points Likert scale question○ Device dysfunction 
Safety
 
○ Adverse Event(s) (AEs) |
| Patient inclusion/exclusion criteria | 
Inclusion criteria:
 
1. Patient is >18 years old,2. Patient for whom a CT-guided procedure in abdomen has been prescribed and agreed by a multidisciplinary team of radiologists, surgeons and clinicians,3. Patient with a confirmed non-opposition. 
Exclusion criteria:
 
1. Patient unable to undergo general anesthesia, 
Pregnant or breast-feeding female
 |
| Visit schedule | 
Schematic diagram of visit schedule:
 
The diagram illustrates the visit schedule with four horizontal arrows representing the timeline. Each arrow is labeled with a visit number and a date range. Below each arrow is a vertical dotted line representing a specific visit. The first visit (Visit 1) is labeled '(D0 - 1m) ≤ D ≤ D0' and is associated with a 'Routine pre-intervention consultation'. The second visit (Visit 2) is labeled 'D0' and is associated with a 'Day of the intervention'. The third visit (Visit 3) is labeled 'D0+3w ≤ D ≤ D0+3m' and is associated with a 'Routine follow-up visit at 2M'. The fourth visit (Visit 4) is labeled 'D0+6m ≤ D ≤ D0+15m' and is associated with a 'Routine follow-up Visit at 10M'.
 
• Visit 1: initial visit – patient screening (D0-1 month) ≤ D ≤ D0 
Review of inclusion and exclusion criteria, presentation of the study and the device (oral and written information for the patient). Paper information
 |

ID RCB : not applicable

Sponsor ID : QS-NIS-G-H-2101

Title of document : Protocol synopsis

Date: 03-OCT-2022

Version: 2.0

| | |
|----------------------------|---|
| | 
notice and non-opposition forms discussed with the patient allowing them sufficient time to consider the study's implications before deciding whether to participate. Next visit planned (day of the CT-guided intervention).
 
• Visit 2: inclusion visit – procedure day D0
- Confirmation of the non-opposition by the investigator,- Collection of demographic data, tumor data, primary cancer data as well as other medical history. Collection of concomitants pathologies/treatments.- Patient placed under general anesthesia.- Acquisition of the pre-interventional CT-guided image for the planning phase.- Insertion of the needle(s) to the targeted area with the subject device.- Acquisition of the per-procedure image under CT guidance.- Validation of the correct positioning of the needle(s).- Acquisition of the post-interventional CT-guided image.• Visit 3: post-intervention follow-up visit at 2 months (D0+3 weeks≤D≤D0+3 months) Acquisition of an image (CT-guided or MRI) of the organ to evaluate ablation site recurrence (local tumor recurrence) and possible AEs.• Visit 4: post-intervention follow-up visit at 10 months (D0+6 months≤D≤D0+15 months) Acquisition of an image (CT-guided or MRI) of the organ to evaluate ablation site recurrence (local tumor recurrence) and possible AEs. |
| Study duration per patient | From patient's information and non-opposition form signature to visit 4. From 6 months to 16 months, depending on the day of patient's non-opposition confirmation and the day of the visit 4. |
| Study schedule | Planned start: Q1 2022 Planned recruitment time: 18 months Planned last patient out: Q1 2024 |
| Randomization/blinding | No randomization, open label |
| DSMB | Non |
| GCP statement | This study will be conducted in compliance with the protocol, the current version of the Declaration of Helsinki, the ICH-GCP and ISO EN 14155 as well as all national legal and regulatory requirements. |

1. INTRODUCTION

The purpose of the Statistical Analysis Plan (SAP) is to describe:

- The statistical methodology.
- The calculated/derived variables.
- The general rules and conventions.
- The tables, figures and listings (TFLs) to be included in the Clinical Study Report (CSR).

The SAP is based on the Clinical Investigation Plan version 2.0 dated 3rd October 2022 and the Case Report Form (CRF) version 2.0 dated 6th May 2022.

2. CLINICAL INVESTIGATION PLAN SUMMARY

2.1. Study objectives

Primary objective:

The primary objective of the study is to describe the performance related to the CT-guided procedure performed with the use of the Quantum Surgical EPIONE® device in the abdomen of the patient.

The primary endpoint is the technical success of each procedure. Technical success is defined in Section 9.1.1. The target is considered to have been reached when the needle(s) is(are) positioned accurately enough to allow the procedure to be carried out.

Secondary objectives:

The secondary performance objectives are as follows:

- Assessment of the needle placement accuracy through an estimation of the distance from the needle inserted and the predefined planning.
- Assessment of the number and the grading of needle readjustments to reach the target (minor, moderate, major).
- Assessment of post-intervention ablation success (ablation only).
- Assessment of the long-term performance of the procedure (local tumor progression rate).
- User satisfaction.
- Assessment of device's dysfunction.

The secondary safety objectives are as follows:

The safety objective is to assess the safety of the device, based on all adverse events (AEs) related to the device or the procedure, including Serious Adverse Events.

The investigator will describe the AE occurrence on a 2-point scale: "no major adverse event related to the CT-guided procedure" or "major adverse event related to the CT-guided procedure".

2.2. Study design

2.2.1. Study design and device

This is a prospective, non-comparative, non-interventional Post Market Clinical Follow-up (PMCF) study.

A total of 55 patients with indication for percutaneous CT-guided procedure in the abdomen will be included at one site in France (Gustave Roussy Institute, Paris) where the EPIONE® device is used routinely.

The operating principle of the investigational device is as follows:

- Pre-interventional CT-scan image acquisition.
- Planning with the device's software (choice of needle(s)' trajectory(ies) to reach the targeted point).
- Needle(s) insertion according to the pre-defined planning.
- Acquisition of a per-procedure CT-scan image to evaluate the needle(s) placement.

Four visits will be recorded in the CRF.

In case of several follow-up visits with the timeslots of Visits 3 and 4, only the last one will be reported in the CRF:

- **Visit 1** (within one month before treatment): the first visit is planned to screen the patient, present the study, and deliver the information notice and informed consent form.
- **Visit 2** (treatment): the second visit consists of recovery of the signed informed consent form, and the realization of the prescribed CT-guided intervention by the radiologist.
- **Visit 3:** Follow-up at 2 months (between 3 weeks to 3 months after treatment).
- **Visit 4:** Follow-up at 10 months (between 6 months to 15 months after treatment), end of study.

Patients who are scheduled for an EPIONE® CT-guided procedure in the abdomen will be enrolled in the study. Eligible patient from the investigator's site will be proposed to participate.

The inclusion period is estimated as 18 months for 55 patients. The study was initiated with the only one site for which the EPIONE® device is routinely used.

2.2.2. Study population

Inclusion criteria

The inclusion criteria are as follows:

- Patient is >18 years old.
- Patient for whom a CT-guided procedure in abdomen has been prescribed and agreed by a multidisciplinary team of radiologists, surgeons and clinicians.
- Patient with a confirmed non-opposition.

Exclusion criteria

The exclusion criteria are as follows:

- Patient unable to undergo general anesthesia.
- Pregnant or breast-feeding females.

[figure not shown]
2.2.3. Study duration and flow chart

Study duration per patient

The study will last from patient's information and non-opposition form signature to Visit 4.

Duration can be 6 months to 16 months, depending on the day of patient's non-opposition confirmation and the day of Visit 4.

Flow chart of the study

2.3. Criteria for evaluation planned in the clinical investigation plan

2.3.1. Primary Variable

The primary objective of the study is the performance of the investigational device.

The performance variable is defined through the technical success of the procedure by the question: "Is/Are the needles positioned accurately enough with the robot to allow next step of the procedure to be carried out".

Frequency and percentage of patients with "Is/Are the needles positioned accurately enough with the robot to allow next step of the procedure to be carried out"= "Yes" reported by the investigator will be described by patient and by procedure.

2.3.2. Secondary Performance Variables

- Needle placement accuracy per needle after adjustments:
 - Estimated distance from the needle tip to expected target point and
 - Estimated distance from the ablation center to targeted ablation center by operators.
- The number of needle adjustments to reach the target and the grading of adjustment
- Post-intervention ablation success using Minimal Ablative Margin (MAM) evaluation.
- Long-term performance of the procedure using the local tumor progression (LTP) rate at around 2 months and 10 months.
- User satisfaction (5-points Likert scale) via 4 questions.
- Device dysfunction (Yes/No)

2.3.3. Secondary Safety Variables

All AEs related to the device or the procedure will be collected.

AEs are categorized in six classes defined below:

Minor complications

- A: No therapy, no consequences.
- B: Nominal therapy, no consequence; includes overnight admission for observation only.

Major complications

- C: Requires therapy, minor hospitalization (< 48 h).

- D: Requires major therapy, unplanned increase in level of care, prolonged hospitalization (> 48 h).
- E: Permanent
- F: Death

If answer is "Major adverse event related to the CT-guided procedure" to the question "Adverse events during procedure" (or AEs classes C, D, E or F in AEs form), the AE will be considered "major" as reported by the investigator.

2.4. Coding

Not applicable.

3. GENERAL ANALYSIS METHODOLOGY

3.1. Study periods

Planned first patient included: Q1 2022

Planned recruitment time: 18 months

Planned last patient completed: Q1 2024

3.2. Definition of protocol deviations

The protocol deviations will be listed by the statisticians when data collection ends. The deviations will then be categorized as major or minor during the interim/final Data Review Meeting (DRM) prior to locking database.

Patients with a major protocol deviation will be excluded from the Per Protocol (PP) population.

3.3. Analysis populations

Four different analysis populations are foreseen:

Screened Population

All patients who are proposed to enter in the study.

Intention-to-Treat (ITT) Population

All screened patients who have confirmed their non-opposition and are planned to be treated using the EPIONE® device.

Per Protocol (PP) Population

All patients in the ITT population treated by the EPIONE® device (including those for which the procedure was not completed with the EPIONE® device) without any major deviation.

Safety Population

All patients in the ITT population treated by the EPIONE® device (including those for which the procedure was not completed with the EPIONE® device).

3.4. Database lock

Interim and final database lock will be executed after resolution of all queries related to data and after the interim/final DRM is held. The interim/final database lock will be performed electronically using ENNOV Clinical V8.0 by the Delta Consultants data management team based on Delta Consultants' SOPs.

3.5. Statistical concerns

The statistical analysis will be performed by an external CRO (Contract Research Organization: Delta Consultants, Eybens, France). All statistical analyses will be produced using SAS® 9.4 software (Cary, NC, USA).

Results will be presented using tables, figures and listings in a Word document.

3.5.1. Summary statistics

Description of relevant study variables will be performed using n, number of missing data, mean, standard deviation, median, min and max for quantitative variables and using number of missing data, frequency and percentage of non-missing for qualitative variables.

Analyses will be presented by patient, by lesion (when relevant) and/or by needle (trajectory). The statistical analysis will take into account data clustering (e.g. several procedures for a given patient) in case of inferential statistics.

3.5.2. Level of significance

A 5% significance threshold will be used.

3.5.3. Adjustments for covariates

No adjustment for covariates is planned for this study.

3.5.4. Handling of dropouts and missing data

Missing data will not be imputed, except dates (missing day) if needed in order to calculate durations.

3.5.5. Multicentre studies

Not applicable since only one site will include patients.

3.5.6. Multiple comparisons/multiplicity

No handling of multiple comparisons will be performed.

3.6. Patient data listings

Individual data listings will be provided in Word format. Patient data listings are listed in Section 13 of this SAP.

4. STUDY PATIENTS

4.1. Disposition of patients

The disposition of patients according to populations of analysis (Screened, ITT, PP, Safety) and visits (Visit 1 – inclusion, Visit 2 – Procedure, Visit 3 – Follow up at 2 months and Visit 4 – Follow-up at 10 months, End of study) will be presented using frequency and percentages.

End of study information (study protocol completed as planned (visit 4), Adverse event, screen failure, patient's willing to withdraw from study, loss to follow-up, device malfunction, death, technical failure, non-feasibility and other) will be presented using frequency and percentages.

4.2. Protocol deviations

Validation of inclusion/exclusion criteria will be presented using frequency and percentages. All protocol deviations will be presented in patient data listings. Major deviations leading to exclusion from PP population will be described as frequency and percentage of patients in the ITT population.

5. DEMOGRAPHIC AND BASELINE CHARACTERISTICS

Demographic and tumor characteristics will be presented on ITT population using summary statistics for qualitative or quantitative parameters:

- Demographic data: age (years), gender, height (cm), weight (kg), Body Mass Index (kg/m²).
- Tumor characteristics: treated organ (liver, kidney or other), type of CT-Guided percutaneous treatment to be planned.
- Planning with the EPIONE device (number of needles trajectories, needle identification information).

Medical history, comorbidities, concomitant treatments and planning with the EPIONE device at inclusion will be described in patient data listings.

6. MEASUREMENT OF TREATMENT COMPLIANCE

Not applicable.

7. PERFORMANCE ANALYSES

Performance analyses will be conducted on the ITT and PP populations.

7.1. Primary endpoint

7.1.1. Definition of the primary variable

The primary endpoint is the technical success of each procedure.

The parameter of the primary endpoint consists of the rate/percentage of robotically assisted needle placements that were accurate enough to allow the percutaneous procedure to be carried on.

The investigator will describe the technical success of the procedure on a 2-point scale:

- “Is/Are the needles positioned accurately enough with the robot to allow next step of the procedure to be carried out” = “Yes”
- “Is/Are the needles positioned accurately enough with the robot to allow next step of the procedure to be carried out” = “No”

The performance endpoint is defined by “Is/Are the needles positioned accurately enough with the robot to allow next step of the procedure to be carried out” = “Yes”.

7.1.2. Statistical evaluation of the primary variable

Performance of the investigational device:

Frequency and percentage of patients with “Is/Are the needles positioned accurately enough with the robot to allow next step of the procedure to be carried out” = “Yes” reported by the investigator will be described by patient and by procedure. A 95% confidence interval will be provided for the percentage.

7.2. Secondary performance endpoints

7.2.1. Needle placement accuracy

Accuracy per needle

This secondary variable evaluates the deviation between the planned and actual needle position once inserted. Operator estimates:

- the 3D distance from the **needle tip** after adjustment(s) to the planned needle tip.
- the 3D distance between **the ablation center** after adjustment(s) and the planned ablation center (if applicable).

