7.2.2. Number of needle adjustments to reach the target and grading of adjustment

This secondary variable records the number and the grading of iterations required to finally reach the target. The number of needle placement adjustments to reach the target will be presented using frequency and percentage per trajectory or per needle, per lesion and per patient.

In addition, grading of adjustment will be presented using frequency and percentage per needle, per lesion and per patient.

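### Does measuring needle accuracy only after adjustment leave SAP 7.2.1 without a valid accuracy result?

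*SAP*

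**What the plan says.** The objective in SAP 2.1 is worded "Assessment of the needle placement accuracy through an estimation of the distance from the needle inserted and the predefined planning" and does not say whether this is before or after adjustment. The protocol synopsis lists needle placement accuracy and needle adjustments as two separate secondary endpoints, also without timing for the first.

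The definitions are specific. SAP 2.3.2 heads the variable "Needle placement accuracy per needle after adjustments". SAP 7.2.1 opens with "This secondary variable evaluates the deviation between the planned and actual needle position once inserted" and then defines two operator-estimated 3D distances: one for the tip, "after adjustment(s) to the planned needle tip", and one for the ablation center, at the same time point.

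Corrections have their own section, SAP 7.2.2: "The number of needle placement adjustments to reach the target will be presented using frequency and percentage per trajectory or per needle", and also per lesion and per patient. It adds that "grading of adjustment will be presented using frequency and percentage per needle, per lesion and per patient". SAP 2.1 gives the grades as minor, moderate and major.

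The protocol synopsis describes the device as an aid to "planning and manual advancement of needle, as well as in verification of needle position".

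**The concern.** A distance measured after correction combines two things: where the device-assisted insertion put the needle, and how far it was moved afterwards. For a needle with no adjustments the recorded distance is the first-pass distance; for an adjusted needle it is not. SAP 7.2.1 and 7.2.2 are reported separately, so a mean distance cannot be attributed to unadjusted or to corrected needles. The opening sentence of 7.2.1, read alone, could lead someone to take the result as first-pass accuracy.

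If needles far from plan are moved closer to it, the reported mean is smaller than the first-pass mean. If the operator follows a target that has shifted from its planned position, it can be larger. The study is single-arm, so there is no comparator to help interpret a mean in millimetres.

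**Working it through.** **1. Is there a contradiction?** Set side by side, the objective in 2.1 and the opening of 7.2.1 leave the time point open, while 2.3.2 and both distances in 7.2.1 fix it as after adjustment. An open statement followed by a specific one is not a conflict. Two analysts reading the whole section would compute the same quantity.

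**2. What can be read from the planned outputs?** The final distance from plan (7.2.1); the share of needles placed with no adjustment, which is the zero row of the frequency table in 7.2.2; and the grade of the corrections. Missing from the visible text are the first-pass distance in millimetres and a breakdown of distance by adjustment count or grade. The Section 13 listings and the CRF were not available, so whether a needle-level listing supplies the link cannot be checked.

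**3. How large could the difference be?** The documents give no figure to reproduce: no accuracy threshold, SD, adjustment rate or adjustment rule. All inputs below are assumptions.

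In millimetres, first-pass mean minus final mean = *a* × (mean reduction among adjusted needles), where *a* is the share adjusted. With *a* from 10% to 40% and reductions of 3 to 8 mm, this runs from 0.1 × 3 = 0.3 mm to 0.4 × 8 = 3.2 mm. With *a* = 0 it is 0.

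A simulation of 1,000,000 needles per scenario used isotropic 3D normal error with SD 2, 3 or 4 mm per axis. The first-pass mean is SD × √(8/π) = 3.19, 4.79 or 6.38 mm. Let *s* be the fraction by which the unadjusted group falls below the first-pass mean, and *r* the residual SD after adjustment divided by the first-pass SD. When needles are adjusted to plan, the pooled final mean falls below the first-pass mean by

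D = (1 − a)·s + a·(1 − r).

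If the farthest needles are the ones adjusted:

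| Share adjusted | Unadjusted group, s | D, r = 1 | D, r = 0.75 | D, r = 0.375 (1.5 mm residual, SD 4 mm) |
|---|---|---|---|---|
| 10% | 9.0% | 8.1% | 10.6% | 14.4% |
| 20% | 15.8% | 12.6% | 17.6% | 25.1% |
| 50% | 33.8% | 16.9% | 29.4% | 48.1% |

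For example, at 10% and r = 0.75: 0.9 × 0.090 + 0.1 × 0.25 = 0.106. The formula agrees with the simulated values to within 0.1 percentage point. At 10% adjusted the range is 0.081 × 3.19 = 0.26 mm to 0.144 × 6.38 = 0.92 mm.

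If adjustment is unrelated to distance, s = 0 and D = a·(1 − r): 0% to 6% at 10% adjusted and 0% to 31% at 50%.

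If needles are adjusted to a target displaced from plan, the sign depends on the displacement. With displacement SD equal to the first-pass SD, the final mean is 0.4% to 2.9% above the first-pass mean at 10% adjusted and 2.8% to 18.2% above at 50%. With displacement SD of 1 mm per axis it is 5.1% to 13.1% below at 10% and 6.7% to 43.2% below at 50%.

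**4. Would splitting the distances by adjustment status recover first-pass accuracy?** When the farthest needles are moved to plan, the unadjusted group is closer to the first-pass mean than the pooled figure only if s < D, that is, if r < 1 − s. The limits are r < 0.91, 0.842 and 0.662 at 10%, 20% and 50% adjusted. With r = 1 the split is further off in every row (9.0% against 8.1%, 15.8% against 12.6%, 33.8% against 16.9%). With r = 0.75 it is slightly closer at 10% and 20% and further off at 50%. With r = 0.375 it is closer throughout, but still 9.0% to 33.8% low.

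**The case for a change.** The best argument for a change is that it costs almost nothing. Distance and adjustment count are both planned data, so a split table needs extra columns and a footnote. It would let a reader tell a small mean achieved at insertion from one achieved by correction. Not knowing the direction in advance can be argued as a reason to report by adjustment status, and a needle-level listing, if one exists, is not a planned summary.

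Part of this stands. The visible text plans neither a first-pass distance nor a breakdown by adjustment, and a split would be informative description. It would recover first-pass accuracy if the choice of needles to adjust were unrelated to distance. But operators have reason to adjust the poorly placed needles, and then the unadjusted group is selected for good placement. Only a distance recorded before the first adjustment closes the gap. That needs a new CRF field or re-measurement on stored images, and the documents do not say that the per-procedure CT precedes every adjustment, so coverage is uncertain.

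A confidence interval for the zero-adjustment share would be a further addition. For the primary rate the SAP states "A 95% confidence interval will be provided for the percentage", and it does the same for local tumor progression and major adverse events, but it promises none for adjustments. With 50 of 55 patients free of adjustment, an assumed count, the exact interval would be 80.0% to 97.0%. That says nothing about distance.

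**Conclusion.** No change to the plan is needed. Followed as written, it gives a sound, openly labelled description of final needle position and a separate description of how much correction was needed. That suits a device meant to help with both placing the needle and checking its position, in a descriptive single-arm study. No objective, threshold or hypothesis relies on first-pass distance, so no planned result is invalid without it. The looser wording in SAP 2.1 and at the start of 7.2.1 is a matter of copy-editing, because the definitions beneath it settle the time point.

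The gap between final and first-pass distance cannot be sized from the documents. The illustrations run from 48% below to 18% above, and the gap is zero if no needle is adjusted; every input to them is assumed. Analysts who wish to show distances separately for needles with none and with one or more adjustments can do so from planned data, provided the unadjusted group is not presented as an unbiased estimate of first-pass accuracy. The conclusion rests on the visible text; the Section 13 listings and the CRF were not seen, and a needle-level listing there would only reduce the gap.
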